6.5.6 Assumption Checks

Convergence of MCMC chains will involve visual comparisons of the trace plots from the 3 chains generated for each model. Quantitative checks such as the Geweke and Gelman/Rubin tests will be completed to ensure convergence to the posterior.

6.5.7 Sensitivity Analysis

In addition to adjusting for level of encephalopathy and center as a random effect, sensitivity analyses may be completed, at the discretion of the Preemie Hypothermia subcommittee, by selecting baseline covariates that differ across the two treatments. These covariates will be selected from those covariates listed in section 5.3. This analysis will only be completed for the primary outcome (death or moderate to severe disability at 18-22 months corrected age) and Death. These sensitivity analyses will be based on the FAS population.

In addition to the FAS population-based analysis, exploratory PP analyses may be done using the PP population on the primary or secondary outcomes at the discretion of the Preemie Hypothermia subcommittee, if the FAS analysis of the primary or secondary outcome results in any clinically notable findings.

6.5.8 Subgroup Analysis

The primary outcome will be reanalyzed for subgroup exploratory analyses. These analyses will be completed using the FAS population. These subgroup analyses will utilize interactions within the risk difference model defined in section 6.5.1 to study treatment heterogeneity and to estimate effects within subgroups when the treatment heterogeneity is clinically important. In each case, the subgroup variable will be added to the model, if not already in the model, along with the interaction between the subgroup variable and the treatment variable. These subgroup analyses will use modified versions of the models that included potentially important covariates and described in sections 6.5.1 and 6.5.2. Only the neutral priors will be considered in these analyses, and the priors for the interaction terms will be the same priors applied to the treatment groups as described in sections 6.5.3 and 6.5.4. In these models with interaction terms, effect coding will be used for treatment and level of encephalopathy instead of reference cell coding.

Reporting of subgroup analyses will include summary statistics from the Posterior distribution of the treatment effect within each level of the subgroup as well as generation of forest plots and posterior plots when deemed useful by the Preemie Hypothermia subcommittee. In addition to estimation of Posterior treatment effects within each level of the subgroup, summary posterior statistics of differences /ratios of treatment effects from all possible combinations of subgroup level pairs will be estimated (possible calculations here will be: differences in differences or ratio of ratios, since they will represent or be functions of effects that make up the interaction term(s) and other combinations not used to create interaction terms in the model given model parameterization). Summary posterior statistics will include medians, 95% credible intervals, and posterior probabilities of benefit.

The subgroups that will be considered are:

- Sex
- Center, if model estimation will allow it
- Race, provided we have sufficient diversity in the study population. At least two levels making up at least 20% each, and at least three levels represented.
- GA (3 levels: 33, 34, and 35 weeks)
- Infants who qualified on seizures alone vs. not (2 levels)
- Infants who had a baseline temperature < 36.5 °C vs. not (2 levels)
- Infants who had a baseline temperature < 35.0 °C vs. not (2 levels)
- Infants who overshot the target and experienced esophageal temperatures < 32.0° C vs. not (an analysis using only babies in the cooling arm) (2 levels)
- Infants who had an abnormal cranial ultrasound after start of intervention but prior to final status will be compared to those who did not (2 levels).
- degree of NE (moderate versus severe)

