2.2 Study Objectives

2.2.1 Study Hypotheses

The risk of death or moderate or severe disability at 18-22 months corrected age will be decreased in infants 33 0/7 - 35 6/7 wks GA and ≥ 1500 grams birth weight with moderate or severe NE due to presumed perinatal hypoxia-ischemia at < 6 hours age who undergo targeted temperature management with whole body hypothermia to 33.5°C (as monitored by esophageal temperature [Tes]) for 72 hours than in those with core temperature (also per Tes) targeted at 37.0°C (controls).

Primary objectives

- 1) To assess differences in death or moderate/severe disability at 18-22 months in enrolled infants randomized to whole body hypothermia for 72 hours, compared to those randomized to normothermia for 72 hours.
- 2) To determine short-term safety (i.e., within 108 hours of baseline [time of insertion of esophageal probe]) of targeted temperature management with whole body hypothermia for 72 hours in infants 33 0/7 -35 6/7 weeks GA with moderate or severe NE at ≤ 6 hours of age. Safety criteria will include serious adverse effects (SAEs): intracranial hemorrhage, cardiac arrhythmia; persistent acidosis;

thrombosis; bleeding; skin changes; necrotizing enterocolitis (NEC); spontaneous intestinal perforation (SIP); esophageal perforation attributable to the placement of the esophageal tube, ulceration or bleeding from the esophageal probe; hypo- and hyperglycemia; receipt of ECMO; thrombocytopenia, and death.

Secondary objectives

To assess differences between study groups with respect to a select set of secondary efficacy and safety outcomes which are listed in Sections 6.2 and 6.3.

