6.5.3 Prior Specification (Binary/Ordinal Primary and Secondary Outcomes)

For the intercept and the encephalopathy terms, Normal(mean = 0, sd=1) priors will be used.

For any other covariates added to the model for sensitivity analyses or any exploratory model, a Normal(mean=0, sd=1) prior will be used.

For the random center effect, we will assume a Normal distribution centered at 0, and the standard deviation parameter will be assumed to follow a half-normal hyperprior with mean equal to 0 and standard deviation equal to 1.

For the term representing the log odds ratio of hypothermia treatment, skeptical, neutral, and enthusiastic priors will be used to estimate posterior distributions for odds ratio when analyzing the primary outcome and primary outcome components. For all other outcomes, only a neutral prior will be used. Because the logistic model will estimate the log odds ratio as the treatment parameter, the priors for the treatment effect will be normal priors on the log odds ratio scale. These normal priors for the log odds ratio are defined below so that the resulting priors in the odds ratio scale have specified properties.

On the odds ratio scale, the skeptical prior for odds ratio will be centered on 1.1 and have a 95% credible interval with an approximate range of 0.28 to 4.40. This skeptical prior will be defined by a normal prior on the log odds ratio scale centered at $\log(1.1) = 0.0953$ with standard deviation (SD) of 0.7072, Normal(mean = 0.0953, sd=0.7072).

On the odds ratio scale, the neutral prior for the odds ratio will be centered on 1.0 and have a 95% credible interval with an approximate range of 0.25 to 4.00. This neutral prior will be defined by a

normal prior on the log odds ratio scale centered at 0 with standard deviation (SD) of 0.7072, Normal(mean = 0, sd=0.7072). Similar priors will be used for the regressions involved in proportional odds modeling of secondary ordinal outcomes.

On the odds ratio scale, the enthusiastic prior for the odds ratio will be centered on 0.75 and have a 95% credible interval with an approximate range of 0.19 to 3.00. This enthusiastic prior will be defined by a normal prior on the log odds ratio scale centered at $\log(0.75) = -0.2877$ with standard deviation (SD) of 0.7072, Normal(mean = -0.2877, sd=0.7072).

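### Baseline temperature is examined as an effect modifier only through two nested yes/no cuts, although one continuous interaction would use more of the information and give a single answer

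*SAP*

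**What the plan says.** SAP section 6.5.8 opens with "The primary outcome will be reanalyzed for subgroup exploratory analyses". Two of the listed subgroup variables come from the same measurement: "Infants who had a baseline temperature < 36.5 °C vs. not (2 levels") and "Infants who had a baseline temperature < 35.0 °C vs. not (2 levels").

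The modelling rule in that section is "In each case, the subgroup variable will be added to the model, if not already in the model, along with the interaction" with treatment, so each cut is fitted in a separate model. The output is "summary statistics from the Posterior distribution of the treatment effect within each level of the subgroup", plus contrasts between levels. On priors the section says "the priors for the interaction terms will be the same priors applied to the treatment groups", using the neutral prior only. For binary outcomes section 6.5.3 sets this as "Normal(mean = 0, sd=0.7072") on the log odds ratio scale.

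The SAP does not say how the two temperature results are to be read together or which takes precedence. Section 6.5.1 already provides for centered continuous coding of added covariates, but no subgroup model uses it for temperature.

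**The concern.** Every infant below 35.0 °C is also below 36.5 °C. An infant between the two cuts is in the cool group of one analysis and in the comparison group of the other, so each contrast pools infants whom the other separates.

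Two things are at stake, both within the exploratory analyses. First, replacing a measurement by a yes/no indicator discards information when the effect changes gradually, and 168 infants give little information about an interaction to begin with. Second, two correlated but different contrasts can leave the reader with one that suggests modification and one that does not, and the plan has no single summary to settle it.

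**Working it through.** The SAP gives no precision or power for any subgroup, so there is no figure of its own to reproduce.

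**1. Information kept by one cut.** Assume a normally distributed temperature and modification linear on the logit scale. With share p below the cut and z the matching normal quantile, the fraction kept relative to the measured value is φ(z)² / [p(1−p)].

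| Share below cut | φ(z) | Fraction kept | Equivalent of 168 infants |
|---|---|---|---|
| 50% | 0.399 | 0.159/0.25 = 0.64 | 107 |
| 30% or 70% | 0.348 | 0.121/0.21 = 0.58 | 97 |
| 10% | 0.175 | 0.0308/0.09 = 0.34 | 57 |
| 5% | 0.103 | 0.0106/0.0475 = 0.22 | 38 |

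The maximum is at the median, so the loss is at least 1 − 0.64 = 36%. The shares are assumptions, because the SAP does not give the temperature distribution.

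**2. Simulated detection.** From the SAP: 168 infants (section 3.4; 84 per arm assumed) and the Normal(0, 0.7072) prior (sections 6.5.3 and 6.5.8). Assumed: temperature mean 36.0 °C and SD 0.9 °C, slope 0.5 log-odds per SD, control log-odds 0.85 (about 70%), treatment log odds ratio −0.6, treatment coded ±0.5. Encephalopathy and center are left out, and the posterior is a normal approximation; 3,000 trials per setting.

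The shares below the cuts are Φ(0.5/0.9) = 0.71 for 36.5 °C and Φ(−1.0/0.9) = 0.13 for 35.0 °C (about 22 of 168 infants). Entries are the percentage of trials in which the interaction points the correct way with posterior probability at least 0.90, a threshold chosen for this check. In the middle row the threshold is instead set separately for each method to give a 10% null rate.

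| Setting | Measured | <36.5 °C | <35.0 °C | Null rates |
|---|---|---|---|---|
| SAP prior, fixed 0.90 | 57 | 25 | 10 | 9 / 3 / 1 |
| SAP prior, equal null rate | 61 | 45 | 38 | 10 / 10 / 10 |
| Wide interaction prior (SD 3), fixed 0.90 | 59 | 44 | 33 | 9–10 / 9 / 9 |

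Simulation error and model details move these by a few points.

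**3. Why the first row overstates the cost of cutting.** A slope of 0.5 per SD corresponds to a yes/no contrast of 0.5 × φ(z)/[p(1−p)]:

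- at 36.5 °C: 0.5 × 0.342/0.206 = 0.83;
- at 35.0 °C: 0.5 × 0.215/0.1155 = 0.93.

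The same prior SD of 0.7072 is applied to 0.5, 0.83 and 0.93, so it shrinks the yes/no contrasts harder. The unequal null rates show the same thing. The second and third rows remove most of this effect.

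**4. How often the two cuts disagree.** Both cuts were applied to the same simulated data (control risk 70%, log odds ratio −0.847, that is 70% to 50% as in the section 3.4 illustration; SAP prior; 5,000 trials per setting). The assumed shares below 36.5/35.0 °C were 40/5, 50/10, 60/20 and 70/30%. The correlation of the two indicators, √[p₂(1−p₁)/(p₁(1−p₂))], is 0.28–0.43 over these pairs.

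| True slope per SD | Opposite signs | Exactly one cut above 0.80 |
|---|---|---|
| 0 | 36–40% | 11–16% |
| 0.4 | 22–32% | 34–41% |
| 0.8 | 7–19% | 32–74% |

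One cut above 0.80 with the other below 0.20 occurs in under 0.5% of trials. The 0.80 limit is borrowed from the benefit criterion in section 3.4; the SAP sets no limit for subgroups.

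**The case against.** The best defence is that modification need not be linear. In the same set-up, with a step of 1.2 log-odds at a cut and equal null rates, the matching cut beats the linear term: 59–62% against 46–49% for a step at 36.5 °C, and 44–47% against 29–30% for a step at 35.0 °C. Section 3.2 makes 36.5 °C the lower bound of the normothermia target, so that contrast has a natural meaning. This stands, and it is why the cuts should be kept as displays. It does not justify leaving out the measured value: the SAP gives no reason to expect a step, and no rationale for 35.0 °C.

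The analyses are also labelled exploratory, and section 6.5.9 would allow a continuous model as an ad hoc analysis. Both are true and keep the severity low. An analysis added after the data are seen carries less weight than one planned now.

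Three stronger readings are tempting and not supported:

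- **The two cuts will contradict each other.** Strongly opposite results are very rare. Opposite signs are mostly noise in weak estimates, and any coolness and marked coolness are different questions.
- **Cutting reduces detection from about 55% to about 25% and 10%.** That is what the SAP's prior yields at a fixed threshold, but part of the gap is prior scaling.
- **The temperature may already reflect the assigned arm.** The SAP defines its safety window as "within 108 hours of baseline [time of insertion of esophageal probe"]. It does not say that the subgroup temperature is taken then, or whether the probe goes in before or after randomization. The protocol may settle this, so it is not an error in the SAP.

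**Conclusion.** The point holds as a low-severity improvement. Section 6.5.8 examines one continuous measurement only through two nested cuts. Under normality and a roughly linear gradient, each cut gives up at least 36% of the information, rising to 66–78% if only 10% or 5% of infants lie below it. At comparable null rates this means about 60% detection with the measured value, against about 45% and 35–40% with the cuts. The practical risk of having two cuts is that one suggests modification and the other does not.

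The temperature distribution, the slope and the thresholds are assumptions. Under a true step at one of the cuts the ranking reverses for that cut. Nothing here affects the primary analysis.

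**What to change.** In section 6.5.8, replace the two temperature bullets by one treatment-by-baseline-temperature interaction, with temperature continuous, centered and scaled per SD, as the main exploratory analysis of this modifier. Report the risk difference and relative risk with 95% credible intervals along the temperature range, including at 35.0 and 36.5 °C. Keep the two cuts as secondary or descriptive displays, with counts per arm. State which temperature is used, and use a pre-randomization value if one is recorded; the example variable list in section 5.3 has no temperature item.

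The cost is a change of SAP wording, with one main model in place of two and no new data collection. The downside is the assumption of an approximately linear gradient: the term is less sensitive than a cut if the true modification is a step at that cut. The retained displays help to reveal such a step.

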- Posterior plot of treatment effect
- Posterior median and posterior standard deviation
- 95% credible interval
- For relative risk, posterior probabilities of >0%, >5%, >10%, and >20% decrease in the primary outcome will be calculated
- For risk difference, posterior probabilities of >0%, >1%, >2%, >3%, and >5% decrease in primary outcome will be calculated
- forest plot of the center level effect and 95% credible intervals.

If the FAS analysis of the primary outcome results in any clinically notable findings, then the primary outcome may also be analyzed in an exploratory fashion using the PP population.

Analysis of Secondary Outcomes

With respect to secondary outcomes, analyses will follow the same process as the primary outcome analysis defined above. See MockTablesAppendix.docx for list of selected variables.

Analysis of Safety (AE) and Hospital Outcomes

Safety and hospital outcomes listed in Sections 6.2 and 6.3 will be analyzed using the FAS population and if necessary, the PP population using relative risk models, proportional odds models, or Negative Binomial models, depending on the type of outcome.

With respect to binary safety outcomes, the estimated posterior distribution of relative risk, θ , based on the data and the neutral prior will be used to determine posterior probabilities of harm from the intervention, $\Pr(\theta > 1 | X)$, as well as 95% credible intervals.

For ordinal safety outcomes, the estimated posterior distribution odds ratio for the cumulative logits, ϕ , will be estimated based on the data and the neutral prior. In addition, posterior probabilities of harm, $\Pr(\phi > 1 | X)$, and 95% credible intervals of ϕ will be calculated.

For count type safety outcome, the estimated posterior distribution of the treatment mean rate, ϕ , will be estimated based on the data and the neutral prior. In addition, posterior probabilities of harm, $\Pr(\phi > 1 | X)$, and 95% credible intervals of ϕ will be calculated.

Analysis of Ultrasound, CT scan, MRI and encephalopathy outcomes

Ultrasound, CT scan, MRI, and encephalopathy outcomes will be analyzed using the FAS population. Head ultrasounds, CT scans, and brain MRIs will be summarized by treatment and time (prior to intervention, during intervention, after intervention, any time). Summaries will be created for number of babies with any abnormal findings during time period data recorded, and for total events across all babies during any time period.

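### SAP 6.5.8 prescribes within-level treatment effects for a subgroup defined by abnormal ultrasound after the start of intervention, and gives the cooling-arm-only overshoot item no exception from the interaction model

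*SAP*

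**What the plan says.** Section 6.5.8 opens by stating their status: "The primary outcome will be reanalyzed for subgroup exploratory analyses". It then gives one method for all of them. "In each case, the subgroup variable will be added to the model" if it is not already there, "along with the interaction between the subgroup variable and the treatment variable". Reporting is to include "summary statistics from the Posterior distribution of the treatment effect within each level of the subgroup", and the summary statistics include posterior probabilities of benefit.

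Two items on the list are defined by what happens after randomization:

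- **Ultrasound:** "Infants who had an abnormal cranial ultrasound after start of intervention but prior to final status", compared with those who did not.
- **Overshoot:** "Infants who overshot the target and experienced esophageal temperatures" below 32.0 °C, with the restriction "an analysis using only babies in the cooling arm".

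Neither item has its own model, a caveat about causal interpretation, or a label as non-randomized.

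Elsewhere the SAP treats the same kind of finding as an outcome. Section 6.2 lists intracranial hemorrhage up to 108 hours as a safety outcome. Section 6.3 lists neurological injury on cranial ultrasound within 24 hours of enrollment as a hospital course outcome. The imaging part of section 6.5.5 summarizes ultrasound findings by treatment and by period ("prior to intervention, during intervention, after intervention, any time"), including abnormal ultrasound and IVH on ultrasound after intervention.

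**The concern.** Randomization makes the arms comparable as whole groups, and within levels of anything fixed before treatment. It does not make them comparable within levels of something that treatment may change. If cooling prevents or causes some ultrasound abnormalities, cooled infants with an abnormal scan are a different mix of risk from control infants with one, and the same applies to infants with normal scans. A treatment effect computed within a level then combines any real effect with that difference in mix. If cooling works by preventing the injury that the scan shows, holding the scan result fixed removes the very effect the trial is looking for.

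Membership also depends on survival. An infant who dies early has less time to show an abnormal scan before final status, and death is part of the primary outcome. The scan due within 24 hours of baseline (section 3.2) lessens this but does not remove it.

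For overshoot, every infant analyzed has the same treatment value, so the general model of 6.5.8 has nothing from which to estimate a treatment effect or an interaction.

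At stake is a published subgroup result, with a probability of benefit attached, that looks like a randomized comparison and is not one.

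**Working it through.** The SAP states no figure on this point, so there is nothing to reproduce. Three checks follow. Their inputs are assumptions, except the 70% control-arm risk (section 3.4) and the priors (section 6.5.3).

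**1. Ultrasound, no treatment effect on the outcome.** Assume half the infants are low-risk (outcome 50%) and half high-risk (90%), in both arms: 0.5 × 0.50 + 0.5 × 0.90 = 0.70. Let a(L) and a(H) be the chance of an abnormal scan in each half.

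- Risk given abnormal = [0.5·a(L)·0.50 + 0.5·a(H)·0.90] / [0.5·a(L) + 0.5·a(H)]
- Risk given normal: the same, with 1 − a in place of a.

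Control arm, a = 20% / 60%:

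- abnormal: (0.05 + 0.27) / 0.40 = 80.0%
- normal: (0.20 + 0.18) / 0.60 = 63.3%

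Cooled arm, a = 5% / 40%:

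- abnormal: (0.0125 + 0.18) / 0.225 = 85.6%, difference +5.6 points
- normal: (0.2375 + 0.27) / 0.775 = 65.5%, difference +2.2 points

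Cooled arm, a = 35% / 60%:

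- abnormal: (0.0875 + 0.27) / 0.475 = 75.3%, difference −4.7 points
- normal: (0.1625 + 0.18) / 0.525 = 65.2%, difference +1.9 points

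The range over the assumed shifts (differences are cooled minus control; the true difference is 0 throughout):

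| Abnormal scans in cooled arm (low / high risk) | Abnormal level | Normal level |
|---|---|---|
| 20% / 60% (no shift) | 0.0 | 0.0 |
| 10% / 50% | +3.3 | +1.0 |
| 5% / 40% | +5.6 | +2.2 |
| 35% / 60% | −4.7 | +1.9 |
| 40% / 70% | −4.5 | 0.0 |

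The second and third rows show apparent harm in both levels. The fourth shows apparent heterogeneity.

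**2. Ultrasound, benefit acting entirely through the scan finding.** Assume the outcome occurs in 90% with an abnormal scan and 50% with a normal one, in both arms. Abnormal scans occur in 50% of controls and 25% of cooled infants.

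- Control: 0.50 × 0.90 + 0.50 × 0.50 = 70%
- Cooled: 0.25 × 0.90 + 0.75 × 0.50 = 60%
- Overall difference: −10 points. Within each level: 90% against 90% and 50% against 50%, so 0.

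**3. Overshoot.** Set up the 6.5.8 model on cooled infants only, with columns for intercept, encephalopathy, treatment, subgroup and treatment × subgroup. That is 5 columns of rank 3: treatment is constant and so repeats the intercept, and the interaction repeats the subgroup term. The data inform only the sums. Under section 6.5.3 the intercept has prior SD 1 and treatment, with the neutral prior, SD 0.7072 (variance 0.50). With treatment coded 1 and center effects set aside, the share of the sum credited to treatment is 0.50 / (1 + 0.50) = one third, whatever the data show. The priors are proper, so software may return a converged posterior, and the convergence checks of section 6.5.6 would not reveal the problem.

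**The case against.** **Overshoot.** The item carries its own restriction, and a specific restriction normally overrides a general rule. With cooled infants only, the one sensible analysis is outcome in those who overshot against those who did not. The rank check shows that the general model cannot be applied literally; it does not show that anyone meant to apply it. This stands. A reader might infer that the SAP plans an inestimable treatment effect here. The text does not support that; it only lacks the exception.

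**Ultrasound wording.** The item speaks of comparing infants with and without an abnormal scan, which could mean exactly that and not arms within levels. But the general rule covers every listed subgroup, and nothing exempts this one.

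**Ultrasound bias.** A reader might infer that the within-level effects are certainly biased, or that a true effect would be reversed. The SAP gives no information on whether cooling changes scan findings, the illustrative errors are zero if it does not, and no calculation above reverses a true effect. What stands is the risk, which the SAP cannot assume away while it compares such findings by arm.

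**Size.** With all 168 infants, assumed 1:1 allocation and 70% risk, the standard error of a risk difference is √(2 × 0.21 / 84) = 7.1 points, and larger within a level. The no-effect errors shown are smaller than that. They are nonetheless as large as the 1 to 5 point decreases for which section 6.5.5 calculates probabilities, and imprecision does not cancel a bias.

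**Consequence.** The analyses are exploratory, use the neutral prior only, and aim at subgroup effects where heterogeneity is clinically important. That limits what is at stake. It does not warn a reader that the comparison is non-randomized, and conditioning on the scan can itself create apparent heterogeneity.

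**Conclusion.** The point holds for the ultrasound subgroup as a risk. Followed as written, section 6.5.8 conditions on a post-randomization variable of a kind the SAP treats as an outcome, and reports treatment effects and probabilities of benefit within its levels without a caveat. Those effects may be biased, or a mediated benefit masked, if treatment changes ultrasound findings. On the assumed inputs the spurious differences run from −4.7 to +5.6 points under no effect, and a 10-point benefit disappears under full mediation. The real size and direction cannot be known from the SAP.

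For overshoot the point is one of wording: the plan already confines the item to cooled infants and should say that the interaction model and treatment-effect reporting do not apply.

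The primary analysis uses neither variable and is not affected. The change should be made, but it is not critical.

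**What to change.** In section 6.5.8:

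1. **Ultrasound.** Remove the item from the subgroups that receive an interaction model and within-level treatment effects. By default, report the association between ultrasound abnormality and the primary outcome, by arm, labelled descriptive and non-randomized, with no probability of benefit. The alternative is to define the subgroup from scans before the start of intervention, a period section 6.5.5 already uses. That answers a different question and may leave few infants, because section 3.2 requires only a scan within 24 hours after baseline.
2. **Overshoot.** State that the interaction and treatment-effect reporting of 6.5.8 do not apply because treatment is constant, and label the item a descriptive, non-randomized comparison within the cooling arm.

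The cost is a few sentences of SAP text. No new data or change to the primary analysis is needed. What is given up is a treatment-effect estimate within ultrasound levels, which would not have had a randomized interpretation.
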